9.1 Subject Disposition

The number and percent of subjects in each of the analysis populations (i.e., ITT, Safety) will be summarized by treatment arm and overall. The number and percent of subjects who enrolled in the study, completed the study, who withdrew from the study and their reasons for withdrawal will be tabulated by treatment arm and overall. Subject disposition will be summarized using all enrolled subjects. Enrolled subjects are those subjects who signed the informed consent form and receive intrathecal hydromorphone supplied by MNK as GMP product for this study.

A listing summarizing whether subjects completed or discontinued from the study will also be presented and the primary reason for discontinuation will be provided for those subjects who withdrew.

9.2 Screening and Baseline Characteristics

9.2.1 Demographics and Baseline Characteristics

Descriptive statistics will be used to summarize demographic and baseline characteristics by treatment arm and for both treatment arms combined. Subject demographics include sex, age, ethnicity, race, height, weight, and body mass index (BMI). Age (in years) will be calculated from the date of birth to the date of informed consent. Age will be reported as an integer. BMI will be calculated using the following formula: BMI (kg/m²) = weight (kg)/(height (m))².

All demographic and baseline characteristics will also be listed.

9.2.2 Medical History

Medical history information will be collected at the Screening visit.

Medical history will be coded using the Medical Dictionary for Regulatory Activities (MedDRA); the dictionary version will be noted in the CSR. Medical history will be summarized by system organ class, preferred term, and treatment arm. Medical history verbatim terms and coded terms will be listed.

Listings will also be provided with the following information:

- History of intractable pain
- Implantation of intrathecal pump and prior opioid use prior to pump implantation
- Surgical intervention(s) for treatment of intractable pain

9.2.2 Medications

Prior medications are defined as medications that were taken within 30 days prior to initial dosing with study drug. Concomitant medications are defined as medications taken any time after the start of dosing until the final visit. Medications are also considered concomitant if their stop date is unknown or marked as continuing. Medications will with missing start dates will be considered ongoing on the first day of study drug administration except where positive confirmation is available that the medication was stopped before study drug administration.

The World Health Organization Drug Dictionary (WHO-DD) will be used to classify prior and concomitant medications by therapeutic class and preferred term. The WHO-DD version will be noted in the CSR. The number and percentage of subjects receiving concomitant medications will be summarized by Anatomical Therapeutic Chemical (ATC) level 3, preferred term, and treatment arm. Subjects will be counted only once for an ATC class and preferred term, even if the subject took the same medication on multiple occasions. Prior medications will be summarized in a similar manner.

A listing of medications will be prepared.

9.2.1 12-Lead Electrocardiogram (ECG)

A safety ECG will be performed at screening to assess any cardiovascular abnormalities for the purpose of determining eligibility for this trial. The number and percentage of subjects with normal, abnormal not clinically significant and abnormal clinically significant ECGs at Screening and Baseline will be summarized.

ECG results will also be listed.

9.2.2 Laboratory Assessments

Blood for chemistry, hematology, and urinalysis laboratory tests will be collected at Screening. The results will be used to determine the subject's eligibility for the study. If abnormal, the investigator will describe the abnormality in the eCRF. Individual laboratory results will not be entered into the eCRF. Abnormal laboratory results (i.e. investigator description of abnormalities) will be listed.

Urine pregnancy tests will also be conducted at Screening and/or Baseline for women of childbearing potential. Pregnancy test results will be listed.

9.3 Study Drug Exposure and Compliance

A listing containing the date and time the current product was removed from the pump, drug concentration, lot number, volume refilled, whether dose adjustments were made, date and time of dose changes, the original and changed daily doses, and whether there were any problems with the pump refill will be listed.

A dosing summary by treatment arm will be presented for the ITT and Safety populations.

9.4 **Protocol Violations**

Violations of the protocol will be recorded appropriately. Examples might include, but not necessarily limited to, the following categories:

- Inclusion/exclusion criteria violation
- Prohibited medication use
- Incorrect treatment or dose
- Treatment non-compliance
- Procedure non-compliance
- Safety observation

Classification of violations from the protocol as minor or major will be decided on a case-bycase basis without knowledge of the treatment assigned and before database lock. A listing of major protocol violations that impact the evaluation of efficacy will be provided.

9.5 Efficacy Analyses

All efficacy endpoints identified in Section 7.1 will be summarized using descriptive statistics by treatment arm (and by visit for secondary efficacy endpoints, where applicable). All summaries of efficacy data will be carried out in the ITT population. All efficacy endpoints will also be listed.

9.5.1 Primary Efficacy Analysis

The primary efficacy endpoint is the proportion of subjects who are treatment failures during the double-blind randomized withdrawal period. After randomization, a treatment failure will be defined by the following criteria:

1. Any subject who experiences an increase of 20 mm or more above the baseline value on a 100 mm VASPI based on the average of 5 days, or

- 2. Any subject who experiences intolerable pain that in the opinion of the investigator requires intervention (i.e. rescue), or
- 3. Any subject who has other interventions for pain that violate the protocol from Day 84 to 119 that includes:
 - a. Requires oral opioid supplement in excess of 60 mg/day morphine-equivalent to manage withdrawal symptoms, or
 - b. Has a change in non-opioid oral prescription medications or nonpharmacological treatments being administered for the management of pain.

Note: A subject who does not have sufficient data for evaluation, drops out for any other reasons that are not listed above or who experiences withdrawal syndrome as identified by COWS > 12 during the double-blind treatment phase will **not** be classified as a treatment failure in the primary efficacy analysis.

The number and percentage of subjects with treatment failure during the double-blind period will be summarized by treatment group. Differences in treatment group failure rates will be test using a Pearson's chi-square (two-sided) test at the 5% level of significance. The corresponding 95% confidence interval for failure rate will be provided.

9.5.2 Secondary Efficacy Analyses

Safety is the most important secondary endpoint. Other secondary endpoints include quality of life / pain scale assessments.

For the purpose of efficacy analyses, 'baseline' will be Day 84.

The change from baseline) to Day 119 in the BPI (pain severity 'worst', pain severity 'average', calculated mean pain severity, and calculated mean pain interference with function.) will be analyzed using an ANCOVA model with treatment group as a factor and the baseline BPI as a covariate. The change from baseline to Day 119 in the SF-MPQ and in oral opioid supplement consumption will also be analyzed using this same type of ANCOVA model.

The distributions of time to rescue will be summarized in each treatment group using the Kaplan- Meier method. Subjects who do not receive rescue medication will be censored at their date of last follow-up. The two groups will be compared using the log rank test.

The PGIC on Day 119 (or at the time of rescue) will be analyzed using the Cochran-Mantel-Haenszel mean score test (using equally spaced scores).

All secondary analyses will be carried out using two-sided tests at the 5% level of significance.

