The purpose of this SAP is to outline the planned analyses to be completed to support the Clinical Study Report (CSR) for Protocol CNS-HYD201US. The planned analyses identified in this SAP will be included in regulatory submissions and/or future manuscripts. Also, exploratory analyses not necessarily identified in this SAP may be performed to support the clinical development program. Any post-hoc or unplanned analyses not identified in this SAP will be clearly identified in the CSR.

Additionally, the purpose of this Amended SAP is to clarify the analyses to be performed as well as the timing of various analyses. During the course of the trial, the Sponsor changed from Mallinckrodt Pharmaceuticals, Inc. (MNK) to Piramal Critical Care, Ltd. (Piramal). As occurs with such changes, the priorities for the study differed from original plans. Piramal made a business decision to proceed with only the safety portion of the study. All subjects completed the study as planned and all data modules pertaining to the safety analysis were cleaned and queried. Efficacy data modules were cleaned and queried up to

11 September 2017, when the decision was made to analyze safety data only. Database lock occurred on 18 October 2017. Subsequently, Piramal made the decision to go forward with the entire analysis of the study. As the study was already unblinded, no further cleaning of the efficacy data modules was permitted. The efficacy analyses will be completed on the locked database, with no changes to the data, unless obvious date errors (i.e., incorrect year resulting in a record incompatible with the study timeline). This Amended SAP describes the updates in conduct and analysis of the trial due to these changes.

3 Study Objectives

The purpose of this clinical study is to demonstrate the efficacy and safety of a 2mg/mL and 10mg/mL formulation of hydromorphone hydrochloride dosed by the intrathecal route of administration in subjects with chronic pain that require continuous opioid treatment through an implantable micro-infusion pump.

Primary Objective

The primary objective of this clinical trial is to demonstrate the superiority of intrathecal hydromorphone hydrochloride in subjects who are on an optimal dose compared with those who have their dose titrated downward during the randomized withdrawal period as measured by treatment failure rate.

Secondary Objective

To evaluate the safety of hydromorphone hydrochloride given by the intrathecal route of administration.

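### Secondary efficacy tests are each run at two-sided 5% with no gate on the primary, order, adjustment or nominal label, so a secondary could be declared significant even if the primary fails

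*SAP*

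**What the plan says.** The primary analysis in SAP 9.5.1 is a single test: "Differences in treatment group failure rates will be test using a Pearson's chi-square (two-sided) test at the 5% level of significance".

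SAP 9.5.2 then sets out the secondary efficacy comparisons:

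- Four BPI measures by ANCOVA: "pain severity 'worst', pain severity 'average', calculated mean pain severity, and calculated mean pain interference with function".
- Two more ANCOVAs: "The change from baseline to Day 119 in the SF-MPQ and in oral opioid supplement consumption will also be analyzed" with the same type of model.
- Time to rescue: "The two groups will be compared using the log rank test".
- Patient Global Impression of Change (PGIC), which "will be analyzed using the Cochran-Mantel-Haenszel mean score test (using equally spaced scores").

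The section ends: "All secondary analyses will be carried out using two-sided tests at the 5% level of significance". Protocol 14.4 carries the same rule but speaks of one BPI change score, where the SAP names four.

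On use of the results, SAP Section 2 says: "The planned analyses identified in this SAP will be included in regulatory submissions and/or future manuscripts". The same section records that the study had already been unblinded when the sponsor decided to go ahead with the full analysis, efficacy included.

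The SAP uses the word exploratory for the by-site subgroup (9.6.5) and for analyses it does not identify (Sections 2 and 8.4). It does not use it for these eight tests. SAP 9.5.2 calls safety the most important secondary endpoint, but that ranks endpoints and gives no testing order for efficacy.

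**The concern.** The plan attaches a significance level to each secondary test but does not say what a significant result may support. Two situations matter.

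- **The primary fails.** Nothing stops a secondary with, say, p = 0.04 from being reported as a significant efficacy finding.
- **The primary succeeds.** Any of eight results may then be presented as significant, each at the full 5%, with no rule on how the set is to be read.

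Because the planned analyses are destined for submissions and manuscripts, the status of these p-values should be stated in the plan and not left to the report.

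**Working it through.** **Inputs**

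- Primary: one chi-square test, two-sided 0.05 (SAP 9.5.1).
- Secondary: two-sided 0.05 per test (SAP 9.5.2, Protocol 14.4).
- Number of tests: 4 BPI + 1 SF-MPQ + 1 oral opioid consumption + 1 time to rescue + 1 PGIC = 8. With BPI counted once, as in Protocol 14.4: 5.
- Correlation among the test statistics: not in the documents, so it is assumed and varied.

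**Step 1. The plan's own figure.** The documents give no family-wise rate for the secondaries. The one related figure is power above 90% for the primary, with 40 per arm and failure rates of 20% and 55%. It reproduces: 91.4% by the pooled normal approximation and 91.5% by exact calculation for the uncorrected Pearson test. The primary is not in question.

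**Step 2. Independent tests, all secondary nulls true.** The chance of at least one p < 0.05 is 1 − 0.95^k.

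- k = 8: 1 − 0.95^8 = 33.7%
- k = 5: 1 − 0.95^5 = 22.6%

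**Step 3. Correlated tests.** Simulated P(max |Z| > 1.96) for equally correlated normal statistics under the same global null, one million draws:

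| Assumed correlation | 8 tests | 5 tests |
|---|---|---|
| 0 | 33.7% | 22.6% |
| 0.3 | 30.0% | 20.9% |
| 0.5 | 25.0% | 18.3% |
| 0.7 | 19.1% | 14.9% |
| 0.9 | 11.9% | 10.1% |

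The BPI measures overlap by construction: SAP 7.2.4 builds mean severity from four items that include worst and average pain. A block structure is therefore more realistic. With 0.8 among the four BPI tests, the rate is 25.7% if all other pairs are at 0.3 and about 22.5% if they are at 0.5.

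**Step 4. What a gate does.** Add the primary as a ninth equally correlated test and count a false secondary finding only when the primary is also significant. Under the global null (primary null also true) this happens in 2.4% of trials at correlation 0.3, 3.1% at 0.5 and 4.2% at 0.8. It cannot exceed 5%, because the primary itself must be significant. If the primary effect is real, the gate opens and the rates in Step 3 apply again to whichever secondaries have no effect.

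**Step 5. What Holm does.** The first step is 0.05/8 = 0.00625, a critical value of 2.734 against 1.960. The chance of any false rejection among the eight under their global null falls to 4.9% if independent and 4.0% at correlation 0.5. For a lone true effect with 80% power at 0.05, power at the first step is Φ(1.960 + 0.842 − 2.734) = Φ(0.068), or about 53%. An effect with 90% power falls to about 69%.

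**The case against.** A reader might infer that the false-positive rate is about 25% where the plan promises 5%. The documents do not support that reading. The 25% needs an assumed common correlation of 0.5, and the 5% is a per-test level. Neither document claims family-wise control over the secondaries.

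A reader might also infer that the plan intends secondary results to rescue a failed primary. No passage says so. The primary objective is measured by treatment failure rate alone, and the only stated secondary objective is safety. Inclusion in a submission is not in itself an efficacy claim.

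Three further points stand:

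- **The count of eight is not firm.** SAP 7.2.3 defines opioid consumption as a total from Day 84 to the end of study, so its change from baseline is not clearly defined. Without it there are seven tests, or 30.2% if independent.
- **The rates assume that no secondary has a true effect.** That is hard to credit for every endpoint if the drug works: rescue for intolerable pain is a component of the primary, and time to rescue is one of the eight.
- **The gate alone deals with the failed-primary case.** The rates in Step 3 are therefore not an argument for Holm in that case.

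These points narrow the size of the problem and the remedy. They leave the omission in place: a declared significance level, on planned tests, with no statement of what a significant result may support.

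**Conclusion.** The concern holds as a gap in the interpretation rule for the secondary efficacy tests. Each is tested at two-sided 5% with no gate, order, adjustment or nominal label, so the plan as written lets a secondary be declared significant even if the primary fails. The primary test's error rate is untouched.

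The size is a range: roughly 12% to 34% for at least one p < 0.05 among eight tests, or about 10% to 23% with BPI counted once. Both ranges are global-null figures over assumed correlations from 0.9 down to 0, in one analysis population. SAP Appendix A lists most of these endpoints again in a second, overlapping population, which would add somewhat if either result could be cited. Even the lowest case is about twice the per-test level, so the need for a stated rule does not depend on the correlation chosen. Confidence is high for the omission and lower for any single figure.

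**What to change.** Replace the last sentence of SAP 9.5.2, and align Protocol 14.4, with:

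> Secondary efficacy tests will be interpreted as supportive only if the primary chi-square test is significant at two-sided 0.05; secondary p-values are otherwise nominal and descriptive and support no claim.

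This needs no new data, patients or analyses. Since the study is already unblinded, the change should be dated and reported as made after unblinding. It only restricts what may be claimed.

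If the sponsor wants formal secondary efficacy claims after a significant primary, add Holm adjustment across the listed tests at a two-sided family-wise 0.05. Holm needs no chosen order, whereas a fixed sequence written now could follow the results. The list should say whether BPI counts as four tests or one, and should define the opioid baseline. The cost is an adjusted p-value column and the loss of power shown in Step 5. A single secondary with an unadjusted p between 0.00625 and 0.05 could then no longer support a claim on its own.

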9.6 Safety Analyses

Safety will be assessed using the Safety population. Safety data will be presented using

summary tables and subject data listings. Safety will primarily be addressed through examination of the incidence and severity of adverse events, as well as, the rate of possible granulomas and the rate of confirmed granulomas. Other safety assessments include vital signs.

9.6.1 Adverse Events

Unless otherwise noted, analyses will be based on treatment-emergent adverse events (TEAEs), defined as those events that begin or worsen in severity after the first treatment with study drug at Baseline. For AEs with missing start dates, the AE will be considered treatment-emergent unless there is additional information indicating that the AE started prior to the first study drug treatment.

Adverse events will be coded to system organ class and preferred term using MedDRA; the dictionary version will be noted in the CSR. AE severity will be assessed and summarized using the Common Terminology Criteria for Adverse Events (CTCAE) v 4.03.

AE incidence tables will include the number and percentage of subject reporting at least one AE, as well as, the number and percentage of AEs summarized by MedDRA system organ class and preferred term. Subjects with two or more AEs in the same system organ class will be counted once for that system organ class; likewise for preferred term. For 'by severity' and 'by relationship to study treatment' tables, subjects will be counted once at the maximum severity and at the strongest causal relationship, respectively. Summaries of treatmentrelated AEs will include those events classified by the investigator as having a possible or probable relationship to study drug (or unknown relationship). Tables will be produced for the following: TEAEs, treatment-related TEAEs, TEAEs by strongest relationship, TEAEs by maximum severity, treatment-emergent serious adverse events (TESAEs), TESAEs by strongest relationship, treatment-related SAEs, and TESAEs by maximum severity. An overall AE summary table will provide top level subject counts for all the AE analyses noted. In addition, the AE summary table will include the number and percentage of subjects reporting any AE (including non TEAEs), the number and percentage of subjects with an AE that led to withdraw of study drug, and the number and percentage of subjects with an AE with outcome of death.

Complete listings of all AEs will be provided (non TEAEs will be flagged with a '*'). In addition, data listings of all SAEs, AEs leading to discontinuation, and AEs leading to death will also be provided.

